8.7 Pharmacokinetic Assessments

8.7.1 Drug Concentration Measurements

Blood PK samples will be collected in Part A only; at time points specified in the PK sampling schedule (Table 2.3). Blood sample collection, processing, and shipping details will be outlined in a separate SRM.

8.7.2 Pharmacokinetic Parameters

The following PK parameter will be determined:

C_{trough} The lowest observed blood concentration prior to next application

All calculations for PK parameters will be based on actual dosing and sampling times recorded during the study. Considering the actual dose received by each patient may vary, the PK parameter will be adjusted by dividing to the actual dose of each patient:

Adjusted PK parameter = C_{trough} / Actual Dose

The actual dosing in each patient will be determined by subtract the weight of each returned study drug and subtract from the initial weight (T_0). In addition, the original blood PK parameter without dose adjustment (C_{trough}) versus time will also be analyzed.

8.8 Safety Assessments

8.8.1 Adverse Events

Patients will be monitored for AEs according to [Section 9](#).

8.8.2 Clinical Laboratory Tests

A certified laboratory will be utilized to process and provide results for the clinical laboratory tests listed in Table 8.1. Clinical laboratory test will be conducted every 2 weeks as indicated in the schedule of assessments ([Table 2.1](#), [Table 2.2](#)). The assessment time for specific tests such as BUN, intact PTH, serum or urine β -hCG, URR, Kt/V is listed in Table 8.1.

The baseline laboratory test results for clinical assessment for a particular test will be defined as the last measurement prior to the first dose of study drug. Blood collection for clinical laboratory tests will be performed before dialysis unless specified in the BUN test in Table 8.1.

During the screening period, if a patient has an out-of-range value for a clinical laboratory parameter that the investigator believes is not clinically significant or the investigator does not believe is correct (eg, lab or specimen processing error), but the investigator wants to confirm with a repeat laboratory test, a single repeat is allowed to confirm the initial result. However, only the final verified data confirmed by the investigator need be recorded in the eCRF.

Additional safety laboratory tests may be conducted as needed by the investigator to evaluate patient safety.

Table 8.1 Clinical Laboratory Tests *

*E

CONFIDENTIAL

For any laboratory test value outside the reference range that the investigator considers clinically significant during the on-study period (ie, following dose administration), the investigator will:

- Repeat the test to verify the out-of-range value and clinical significance but only the final verified data confirmed by the investigator need be recorded in the eCRF.
- Follow the out-of-range value until the value returns to normal or baseline, or until the value is deemed stable and not clinically significant by the investigator.
- Record as an AE any laboratory test value that is confirmed by repeat and the investigator considers clinically significant, requires a patient to be discontinued from the study, requires a patient to receive treatment, or requires a change or discontinuation of the study drug (if applicable).

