8.8.4 Vital Signs

Vital signs assessments will include temperature ($^{\circ}\text{C}$), respiratory rate (breaths per minute), systolic and diastolic blood pressure (mmHg), and pulse rate (bpm). Vital signs will be measured after the patient has been resting quietly in a seated position for at least 5 minutes. Any clinically significant abnormal vital sign assessment requires at least one repeat measurement but only the final verified data confirmed by the investigator need be recorded in the eCRF.

A vital signs abnormality that is considered clinically significant initially and on confirmation, requires a patient to be discontinued from the study, requires a patient to receive treatment, or requires a change or discontinuation from the study drug (if applicable) will be recorded as an AE.

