10.6 Safety Analysis

All safety analysis will be performed on the SAS for both Part A and Part B.

Adverse events will be coded by System Organ Class and Preferred Term using the current version of MedDRA. Incidences of TEAEs (ie, events that started after 1st dose of the study drug or worsened in severity after 1st dosing), will be presented by dose group. Incidences of TEAEs will also be presented by maximum severity and relationship to study medication.

Safety data will be summarized through appropriate data tabulations, standard descriptive statistics, and graphical presentations. For each continuous laboratory parameter, results will be categorized as low, normal, or high based on the laboratory normal ranges. Frequencies and percentages will be presented by dose group for patients who had a shift to low and for patients who had a shift to high from baseline to any post-dosing assessment.

The association of AEs, clinical laboratory tests, vital sign measurements with the actual dosing of the study drug or systemic exposure of LT5001 drug product may also be explored. If appropriate, statistical modeling will be performed to further characterize the associations mentioned above. All out-of-range and clinically significant laboratory results will be identified in patient data listings. The number and percentage of patients in each dose group with normal and abnormal physical examination results will be presented for evaluations at baseline and final visit.

For each body system, changes in the patients' findings from baseline to final visit (no change, normal to abnormal, or abnormal to normal) will be tabulated for each dose group.

Application site examination (observed and change from baseline) will be summarized by time point using appropriate descriptive statistics.

The number and percentage of patients reporting any treatment-emergent AE will be tabulated by system organ class and preferred term (coded using MedDRA). Treatment-emergent AEs will be further classified by severity and relationship to treatment.

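### On-study repeats of clinically significant laboratory values and vital signs need only the final value in the eCRF, which cannot guarantee the listings and shift tables that the plan promises

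*Protocol*

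**What the plan says.** Protocol 8.8.2 sets the on-study laboratory rule. The trigger is stated as "For any laboratory test value outside the reference range that the investigator considers clinically significant during the on-study period". The investigator must then run the test again to check the value and its significance. The recording duty is limited: "only the final verified data confirmed by the investigator need be recorded in the eCRF". The AE instruction in the same list covers a value that is confirmed by repeat and judged clinically significant, and also names discontinuation, treatment and a change of study drug.

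Protocol 8.8.4 has the same recording rule for vital signs. The trigger is: "Any clinically significant abnormal vital sign assessment requires at least one repeat measurement". As with laboratory tests, the eCRF has to hold no more than the final verified value. The number of repeats is not capped. A vital-sign abnormality becomes an AE if it is significant both at first and on confirmation, or if it leads to one of those three consequences.

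On the analysis side, Protocol 10.6 states: "All out-of-range and clinically significant laboratory results will be identified in patient data listings". It also counts patients with a shift to low or to high between baseline and any assessment after dosing. SAP 11.4 tabulates laboratory shifts by visit, both as normal, abnormal not clinically significant (NCS) and abnormal clinically significant (CS), and as low, normal and high. SAP 11.3 summarises vital signs by visit. The visible SAP text has no rule for initial, repeat or unscheduled values.

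Screening has its own laboratory repeat rule in Protocol 8.8.2: "a single repeat is allowed to confirm the initial result". Its trigger is a value that the investigator thinks is not clinically significant or is incorrect.

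**The concern.** The re-measurement is selective. On study, a clinically significant abnormal value must be measured again, while no rule asks for a normal value to be re-measured. If only the final value is entered, the dataset can move from abnormal to normal through this rule but not the other way. Some repeats return to range through measurement noise or within-patient variation. Others do so because a real abnormality after dosing was short-lived. The rule does not separate these cases from each other or from a laboratory error.

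The affected outputs are the laboratory listing, the shift counts and the by-visit vital-sign summaries. Protocol 5.1.1 includes vital signs and laboratory results in the data that the DSMB reviews before Part B, when only 12 patients have been allocated to LT5001 (synopsis, Sample Size). With so few patients, one unrecorded value could be noticeable, although the documents give no rate from which to expect one.

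**Working it through.** The plan states no figure on this point, so there is nothing to reproduce. The check has two parts.

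**1. Following a value through the rules**

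| First on-study value | Needed in eCRF | AE page | Protocol 10.6 listing and shifts (laboratory) |
|---|---|---|---|
| Out of range, judged not clinically significant | Yes; no repeat triggered | Not by this rule | Complete |
| Clinically significant, confirmed by repeat | Final (abnormal) value | Yes | Abnormality appears |
| Clinically significant, not confirmed, but treated or study drug changed | Final value only | Can be reached through the listed consequences | First value may be missing |
| Clinically significant, not confirmed, no action | Final value only | Not required by 8.8.2 or 8.8.4 | First value may be missing |

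The gap is in the last row and, for the laboratory listing only, in the third. SAP 5.2 does not impute safety values, so the analysis cannot recover what was not entered. The conflict with the 10.6 listing concerns laboratory results. For vital signs, the effect is on the SAP 11.3 summaries.

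**2. How large the loss could be (assumptions only)**

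Let the first value X1 and the repeat X2 be standard bivariate normal with test-retest correlation ρ. The reference limit is L = 1.96 SD, and clinical significance begins at t ≥ L. The share of repeats back in range is

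P(X2 ≤ L | X1 > t) = ∫ from t to ∞ of φ(x) Φ((L − ρx)/√(1 − ρ²)) dx ÷ (1 − Φ(t)).

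| Clinical significance begins at | ρ = 0.7 | ρ = 0.85 | ρ = 0.9 |
|---|---|---|---|
| 1.96 SD (every exceedance repeated) | 67% | 49% | 41% |
| 2.5 SD | 49% | 23% | 12% |
| 3.0 SD | 32% | 7% | 2% |

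The first row is an upper end, because it treats every value beyond the reference limit as clinically significant. The model also centres patients on the reference range. If a parameter in dialysis patients is centred 1 SD higher (assumption), the first row falls to 46%, 33% and 27%. The table does not count repeats that stay out of range but are downgraded from CS to NCS.

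For Part A, assume that 5% of patients on LT5001 have a clinically significant first value. The chance of at least one among 12 is 1 − 0.95^12 = 46%. If a share r of these is lost, the recorded rate is 0.05 × (1 − r):

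- r = 2%: 1 − (1 − 0.049)^12 = 45%
- r = 50%: 1 − (1 − 0.025)^12 = 26%
- r = 67%: 1 − (1 − 0.0165)^12 = 18%

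**The case against.** The case against has five parts.

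- **The wording sets a minimum.** It says what need be entered and does not forbid entering the first value. Verification may also uphold the first result. This stands: a reader might infer that first abnormal values always disappear, and the text does not say that. But a permissive rule lets sites differ, so completeness is still not assured.
- **First results survive elsewhere.** Protocol 14.1.2 and 14.1.3 keep laboratory reports as source, and monitors check eCRF entries against medical records (12.3). The general AE definition in Section 9 could also capture a transient sign. This stands too: the possible loss is from the analysis database, not from all records. Listings and tables are nevertheless built from that database.
- **The screening repeat is different.** It is triggered by values thought not clinically significant or wrong, and setting aside an error is legitimate. SAP 5.3 takes Day 1 laboratory data as baseline, so this branch hardly touches the safety tables. Accepted.
- **Both blinded arms follow the same rule.** With a common loss share, the ratio of rates is unchanged. That is correct, but both counts and the absolute difference shrink. For example, assumed rates of 20% and 5% with half lost become 10% and 2.5%, and the difference falls from 15 to 7.5 points.
- **Some material cannot be seen.** The content of Table 8.1, part of SAP 11.4 and the CRF are unavailable, so capture of repeats may be specified there. This limits the point to the text that can be read.

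**Conclusion.** The point holds as a mismatch between a recording rule and the outputs promised from it. Under Protocol 8.8.2 and 8.8.4, a clinically significant on-study value that was not confirmed and needed no action may be missing from both the safety dataset and the AE page. The listing and shift counts in Protocol 10.6 and the CS category in SAP 11.4 then cannot be guaranteed complete, and any loss is towards normal. On-study values that are out of range but judged not clinically significant are unaffected.

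The size is unknown. The range of about 2% to 67% rests on the bivariate normal model, correlations of 0.7 to 0.9, and a clinical-significance threshold between 1.96 and 3.0 SD. None of these comes from the documents.

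A reader might infer two stronger conclusions, and neither is supported. One is that around half of repeated abnormal values will drop out of the tables. That figure needs nearly every exceedance to be judged clinically significant, or a low correlation. The other is that the recording rule biases the Part A primary endpoint. That endpoint is adverse events, and a separate confirmation rule decides which laboratory values and vital signs become AEs. Entering both values would not change it.

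**What to change.** In Protocol 8.8.2 and 8.8.4, require the initial value and every repeat on-study value in the eCRF, each flagged as initial or repeat, with a laboratory or specimen error marked where it is documented.

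In SAP 11.3 and 11.4, state that listings, and laboratory shifts at any assessment after dosing, use all valid values and exclude only documented errors. Pre-specify one value per visit for the by-visit summaries. Protocol 10.6 can then stand as written.

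The cost is one extra eCRF row per repeat and a sentence or two in each document. There is no new patient procedure and no change to clinical management. The small downside is that some unconfirmed abnormal values will appear in the listings, where the flag identifies them.

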8.8.3 Other Tests

The following test history will be reviewed or performed:

- History of latest serology test (ie, HBsAg, HCV antibody, and any confirmatory tests performed at the discretion of the investigator)
- History of HIV
- Serum or urine β -hCG test (females only)

8.8.4 Vital Signs

Vital signs assessments will include temperature ($^{\circ}\text{C}$), respiratory rate (breaths per minute), systolic and diastolic blood pressure (mmHg), and pulse rate (bpm). Vital signs will be measured after the patient has been resting quietly in a seated position for at least 5 minutes. Any clinically significant abnormal vital sign assessment requires at least one repeat measurement but only the final verified data confirmed by the investigator need be recorded in the eCRF.

A vital signs abnormality that is considered clinically significant initially and on confirmation, requires a patient to be discontinued from the study, requires a patient to receive treatment, or requires a change or discontinuation from the study drug (if applicable) will be recorded as an AE.

8.8.5 Physical Examination

At Screening, comprehensive physical examinations (excluding genital, rectal, and breast examinations [unless indicated] will be performed. In addition, physical examination of the skin will be conducted as a full-body skin assessment, which will serve as subject's baseline skin condition. Abnormal findings will be documented in the patient's eCRF. The investigator may consider photograph the skin condition of the treatment area upon his/her judgement (optional). Subject's baseline skin condition will be used as reference for comparison in the application site examination.

Targeted symptom-driven physical examinations will be performed on Day 1, 3, 6, 8, 15, 22, and 29 of each treatment period and at the end-of-study visit.

An abnormal physical examination finding that is considered clinically significant and requires the patient to be discontinued from the study, requires the patient to receive treatment, or requires a change or discontinuation of the study drug (if applicable) will be recorded as an AE.

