8.8.6 Application Site Examination

Application Site Examination will be conducted at Visit 2 to 8 in Part A and Visit 2 to 9 in Part B as indicated in schedule of assessment ([Table 2.1](#), [Table 2.2](#)). Application site evaluation will be conducted by comparing the skin of the application site with the baseline skin condition in each visit.

The application site evaluation will include dermatitis, pruritus, paresthesia, erythema, dryness, vesicles, irritation, papules, burning assessed by ICDRG scale (Table 8.2). An abnormal application site finding that is considered clinically significant will be recorded as AE. The investigator may consider photograph the skin condition under the consent of the subject if the investigator considered helpful for the safety assessment in the DSMB meeting (optional).

Table 8.2 Grading score by International Contact Dermatitis Research Group (ICDRG)

Grading	Morphology	Interpretation
-	No reaction	Negative
±?	Erythema only, no infiltration	Doubtful reaction
+	Erythema, infiltration, possibly discrete papules	Weak positive reaction
++	Erythema, infiltration, papules, vesicles	Strong positive reaction
+++	Erythema, infiltration, confluent vesicles	Extreme positive reactions
Ir	Different types of reactions (dermatitis, paresthesia, dryness, burning)	Irritant reaction

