9 ADVERSE EVENTS

An AE is defined as any untoward medical occurrence in a patient administered a pharmaceutical product during the course of a clinical investigation. An AE can therefore be any unfavorable and unintended sign, symptom, or disease temporally associated with the use of a study drug, whether or not thought to be related to the study drug.

Each AE will be collected from the signing of the ICF until the follow-up/end-of-study visit. Adverse events that are identified at the last assessment visit (or the early termination visit) must be recorded on the AE eCRF with the status of the AE noted. All events that are ongoing at this time will be recorded as ongoing on the eCRF. If the Investigator indicates the AE is “probably”, “possibly”, or “definitely” related to the study drug, the AE must be followed until they are resolved or medically stable, or until reasonable attempts to determine resolution of the event are exhausted. The investigator should use his/her discretion in ordering additional tests as necessary to monitor the resolution of such events.

The procedures specified in [Section 9.4](#) are to be followed for reporting SAEs.

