9.2.2 Intensity

The intensity of an AE will be graded according to the following definitions:

- Mild: The patient experiences awareness of symptoms but these are easily tolerated or managed without specific treatment.
- Moderate: The patient experiences discomfort enough to cause interference with usual activity, and/or the condition requires specific treatment.
- Severe: The patient is incapacitated with inability to work or do usual activity, and/or the event requires significant treatment measures.

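### Protocol 8.8.5 makes clinical significance plus an action the AE-recording rule for physical-examination findings, narrower than the neighbouring rules and Section 9, so AEs may be under-recorded

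*Protocol*

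**What the plan says.** Protocol 8.8.5 sets the recording rule for physical-examination findings. The sentence opens: "An abnormal physical examination finding that is considered clinically significant and requires the patient to be discontinued from the study, requires the patient to receive". The finding must be clinically significant and must also lead to at least one of three things: withdrawal from the study, treatment, or a change or stop of study drug. The section does not contain the word *only*. After screening these examinations are limited in scope: "Targeted symptom-driven physical examinations will be performed on Day 1, 3, 6, 8, 15, 22, and 29" and at the end-of-study visit.

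The other assessment sections are wider.

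- Laboratory values, 8.8.2: "Record as an AE any laboratory test value that is confirmed by repeat and the investigator considers clinically significant, requires a patient to be discontinued", followed by the remaining actions in an *or* list.
- Vital signs, 8.8.4: "A vital signs abnormality that is considered clinically significant initially and on confirmation, requires a patient to be discontinued from the study", again followed by the other actions in an *or* list.
- Application site, 8.8.6: "An abnormal application site finding that is considered clinically significant will be recorded as AE".
- Repeated open application test, 8.2: an ICDRG grade of + or more that is clinically significant is an AE, with no action needed.

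Section 9 gives the general definition: "An AE can therefore be any unfavorable and unintended sign, symptom, or disease temporally associated with the use of a study drug". It adds that each AE is collected from consent to the end of follow-up. Section 9.2.2 provides a Mild grade: "The patient experiences awareness of symptoms but these are easily tolerated or managed without specific treatment".

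**The concern.** The nature and severity of AEs and the number of patients with AEs form the Part A primary endpoint (Protocol 10.4.1) and a Part B secondary endpoint (10.4.4). SAP 11.1 tabulates whatever was recorded as a treatment-emergent AE and does nothing to reconcile the recording rules.

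Physical examination is the only assessment whose AE sentence adds a mandatory action. The action lists in 8.8.4 and 8.8.5 are almost identical, which suggests that the *and* is a drafting slip, but it changes the meaning. Site staff completing the examination page are likely to take 8.8.5 as the working rule, because a significant finding that needs treatment is already an AE under Section 9 and the sentence adds nothing unless it is a threshold.

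If it is used that way, significant findings that need no action may not reach the AE page. Part A has one site, so the risk there is undercounting. Part B has four (SAP 5.1), so different sites could also treat the same finding differently.

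**Working it through.** No arithmetic decides this point, and the plan gives no figure to reproduce. The check is to set the rules side by side.

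| Source | Is clinical significance enough without an action? |
|---|---|
| 8.8.2 laboratory | Yes, once confirmed by repeat; the actions are alternatives |
| 8.8.4 vital signs | Yes, once confirmed; the actions are alternatives |
| 8.8.6 application site | Yes |
| 8.2 open application test | Yes, at ICDRG + or more |
| Section 9 definition | No action condition, and no significance condition either |
| 8.8.5 physical examination | No; an action is also required |

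**Step 1: which findings are exposed.** SAP 11.5 lists general appearance, skin, head and neck, chest and lung, heart, abdomen, extremities, neurologic system and other. Skin at the application site is covered by 8.8.6, and the open-application zone by 8.2. For the other body systems, and for skin away from treated areas, 8.8.5 is the only assessment-specific AE rule.

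**Step 2: which severities are exposed if 8.8.5 is used as the threshold.** Under 9.2.2 a mild event is managed without specific treatment. A mild finding would then enter through 8.8.5 only if study drug were changed or stopped, or the patient withdrawn. A moderate event is defined by interference with usual activity and/or a need for specific treatment. One that qualifies through interference alone, with no drug change or withdrawal, would also miss. So mild findings and some moderate ones are exposed.

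**Step 3: the same findings read together with Section 9.** Section 8.8.1 sends AE monitoring to Section 9, which has no action condition and collects each AE. On this reading every finding in Step 2 is still an AE and stays in the endpoint. The two readings give different AE counts from the same examination.

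**Step 4: what would be visible.** SAP 11.5 tabulates Normal, Abnormal NCS and Abnormal CS by visit, with shifts from baseline and a by-subject listing. Under the threshold reading the report could show shifts to Abnormal CS with no matching AE.

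**Step 5: size.** In Part A one patient is 1/12 = 8.3 percentage points on LT5001 and 1/6 = 16.7 points on placebo. These figures show how coarse the patient count is; they do not estimate the loss. They apply only if the missed finding is that patient's sole AE. Otherwise the number of patients with any AE does not change, although event counts and severity tables could.

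**The case against.** The strongest reply is that 8.8.5 gives a sufficient condition, not an exclusive one. It says that findings of a certain kind will be recorded and excludes nothing, while Section 9 governs and requires each AE to be collected. This stands. A reader might infer that an examination finding is an AE only if it forces an action, and that mild findings therefore drop out of the Part A primary endpoint. The documents do not support that as a statement of what the plan requires. It is a risk that arises if a site uses 8.8.5 as its threshold.

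A reader might also suppose that the same new rash would be an AE under the application-site examination and not under the skin item of the physical examination. That does not hold for treated skin: such a rash meets 8.8.6 on clinical significance alone, wherever else it is noted. A rash away from treated skin is not an 8.8.6 finding, so it is a different case. Application-site and open-application reactions are not exposed.

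Two further limits stand. Later examinations are symptom-driven, so the prompting symptom may itself be recorded as an AE under Section 9. And the findings would not be lost, because SAP 11.5 reports them and a mismatch could be queried.

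None of this removes the inconsistency. Five other parts of the protocol set no action condition, one sentence does, and nothing tells the site which prevails.

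**Conclusion.** The concern holds as an internal inconsistency with a plausible but limited effect. The AE sentence in 8.8.5 is narrower than 8.2, 8.8.2, 8.8.4, 8.8.6 and Section 9. A site that relies on it may not record clinically significant examination findings that needed no action, including mild and some moderate ones.

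This rests on one assumption: that some staff will apply 8.8.5 as the operating rule for examination findings. If they apply Section 9 throughout, nothing is lost. The exposure is confined to findings outside the application site and the open-application zone.

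The undercount cannot be estimated, since the documents give no expected rate of such findings, and the one-patient percentages should not be read as its size. The documents also do not support a claim that such findings are never counted. The change is nonetheless worth making, because it protects a primary endpoint at almost no cost.

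**What to change.** Reconcile 8.8.5 with 8.8.2, 8.8.4, 8.8.6 and Section 9 by replacing the *and* with an *or* list. A possible wording: *A physical-examination abnormality is recorded as an AE if the investigator judges it clinically significant, or if it leads to treatment, to a change or stop of study drug, or to withdrawal from the study. This sentence does not limit the AE definition in Section 9.*

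The second sentence is needed because the list still refers to clinical significance, which Section 9 does not. Without it, a mild sign judged not clinically significant could still be thought excluded.

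The change concerns recording only and leaves treatment decisions untouched. The cost is a one-sentence protocol correction and a reminder to sites. The downside is that the reported AE count may rise slightly.
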